Two-sided 95% confidence intervals using Hodges-Lehman method will be additionally calculated. Survival analyses using Kaplan-Meyer estimates and plots, log-rank test and Coxregression modeling will serve as sensitivity analyses.

For survival analyses, different sets of analyses will be done:

- (1) The composite variable for subjects without any mechanical ventilation and without any use of inotropes is set to 0, observations will not be censored
- (2) The composite variable for subjects without any mechanical ventilation and without any use of inotropes is set to 0, observations will be censored
- (3) Subjects without any mechanical ventilation and without any use of inotropes will be deleted from analysis

Subjects who receive mechanical ventilation or are still using inotropes on the last day of observation (which can be Day 28, day of early discontinuation, or day of death) will be censored for survival analyses.

Analysis of Secondary Efficacy Endpoints

No formal statistical hypotheses are specified for the secondary endpoint variables. Nonetheless statistical testing methods will be applied to compare treatment groups. A significance level of 5% (two-sided) will be used for such analyses. Secondary efficacy endpoints will be analyzed using the FAS, mFAS and the PP.

Length of Time on Mechanical Ventilation

The same definitions and analyses as described for the primary endpoint will be applied.

Length of Time on Positive Pressure Ventilation

The same definitions and analyses as described for the primary endpoint will be applied.

Length of Time of Inotrope Use

The same definitions and analyses as described for the primary endpoint will be applied.

Inotrope Score

The total inotrope score at each hour post-operatively from the time of separation from bypass, until the completion of study drug will be calculated as:

Total Inotrope Score = Dopamine + Dobutamine + 10*Milrinone + 100*Epinephrine + 100*Phenylephrine + 100*Norepinephrine.

The total inotrope score will be summarized at each post-operative hour and analyzed using a Wilcoxon-Rank sum test and an analysis of variance (ANOVA) with a fixed effect for treatment group. Also, a repeated measures analysis of variance will be used to compare total inotrope score between placebo and L-citrulline over time.

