Survival analyses using Kaplan-Meier estimates and plots, log-rank test (significance level of 5%) and Cox-regression modeling including factor treatment (no further factors to be included) will serve as sensitivity analyses. For subjects who died before discharge from the hospital or before Day 28, respectively, the observed length of time on mechanical ventilation/inotropes will be used. The sensitivity analyses (1) and (2) as described for the primary analysis (subjects who died will (1) be excluded from analysis and (2) be assigned a length of time on inotropes of 28 days) will not be applied for survival analyses. The sensitivity analyses (3) and (4) as described for the primary analysis (composite endpoint will be derived with (3) length of time of inotrope use starting on first "start date/time" of inotrope use and (4) length of time of inotrope starting on first "start date/time" of inotrope use and length of time on mechanical ventilation starting on "start date/time" of mechanical ventilation) will be applied for survival analyses. For survival analyses different sets of analyses will be done:

(1) The composite variable for subjects without any mechanical ventilation and without any use of inotropes is set to 0, observations will not be censored

(2) The composite variable for subjects without any mechanical ventilation and without any use of inotropes is set to 0, observations will be censored

(3) Subjects without any mechanical ventilation and without any use of inotropes will be deleted from analysis

For sensitivity analyses (3) and (4) the first set of analyses (i.e., (1) The composite variable for subjects without any mechanical ventilation and without any use of inotropes is set to 0, observations will not be censored) will be used.

Subjects who receive mechanical ventilation or are still using inotropes on the last day of observation (which can be Day 28, Day of early discontinuation, or Day of death) will be censored for survival analyses.

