For the length of time on vasodilators the same analyses as described for the primary endpoint will be applied.

Length of hospitalization

The length of hospitalization will be calculated as the total number of days postoperative until discharge from the hospital. The length will be derived as the number of days from day after surgery (variable "Date of surgery" on CRF "Surgery" + 1) until discharge from the hospital (variable "Hospital Discharge date" on CRF "End of study").

- Length of hospitalization (days) =
Hospital Discharge date - (Date of surgery + 1) + 1

For subjects who died before discharge from the hospital or before Day 28, respectively, the observed length of hospitalization will be used. As sensitivity analyses subjects who died will (1) be excluded from analysis and (2) be assigned a length of hospitalization of 28 days.

For the length of hospitalization, the same analyses as described for the primary endpoint will be applied.

Thoracotomy output - duration and volume of chest tube drainage

The total postoperative duration (in minutes) that the chest tube will be used will be calculated as the time from the end of the surgery (variables "Date of surgery" and "End time" from section/CRF "Surgery") to the time the chest tube will be removed (variable "Date/time of removal" from section/CRF "Thoracotomy Output").

If an additional chest tube is required or reinserted (until discharge from the hospital or at Day 28) the duration that the additional chest tube was used (from time of insertion to time of removal) will be added to the time the original chest tube was used for the total postoperative duration.

- Length of chest tube drainage (min) =
(Time removal - End time (surgery) + 1) +
(Time removal (second assessment) - Time reinsertion + 1)

If a subject did not use any chest tube the duration is set to 0. As a sensitivity analysis, subjects with no use of chest tube will be excluded. For subjects who died before discharge from the hospital or before Day 28, respectively, the observed duration of chest tube drainage will be used.

For the total postoperative duration, the same analyses as described for the primary endpoint will be applied.

Again, as sensitivity analyses subjects who died will (1) be excluded from analysis and (2) be assigned a length of time of chest tube placement of 28 days.

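### The survival analyses of the primary composite censor death on support and drop the 28-day rule for deaths, so none of them measures coming off support alive

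*SAP*

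**What the plan says.** The primary test is a two-sided 1% Wilcoxon rank-sum test on the longer of ventilation time and inotrope time. The survival methods support it: "Cox-regression modeling including factor treatment (no further factors to be included) will serve as sensitivity analyses" (SAP 4.4.1).

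SAP 4.4.1 treats deaths as follows.

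- **Wilcoxon test.** Deaths enter with their observed length. Two sensitivity analyses are kept: (1) exclude children who died, and (2) assign them 28 days.
- **Survival analyses, censoring.** The rule covers "Subjects who receive mechanical ventilation or are still using inotropes on the last day of observation", a day "which can be Day 28, Day of early discontinuation, or Day of death) will be censored for survival analyses". Death on support is thus handled like reaching Day 28 or leaving the study early.
- **Survival analyses, death rules.** Analyses (1) and (2) are both withdrawn. For (2) the text reads "be assigned a length of time on inotropes of 28 days) will not be applied for survival analyses".

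Protocol 7.1.4 has the same censoring sentence ("which can be Day 28, day of early discontinuation, or day of death) will be censored for survival analyses") and the same two death rules, but nothing that withdraws them for the survival analyses. SAP section 5, Changes from Protocol, does not mention the withdrawal. Neither document plans a competing-risk analysis. Otherwise deaths appear as an exploratory 28-day percentage (SAP 4.6) and in the tables of adverse events leading to death (SAP 4.5).

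PICU stay and hospital stay reuse the primary analyses. For a child who dies before hospital discharge, "the observed length of hospitalization will be used" (SAP 4.4.2).

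**The concern.** In these analyses the event is the end of ventilation and inotropes. A child who dies on support can no longer have that event. Censoring at death is harmless to the curve only if the child would have gone on to come off support like those still at risk, which cannot be true of a child who has died.

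The objective is a reduced need for postoperative support. A reader of the Kaplan-Meier plot will take its complement as the proportion of children who came off support by a given time. With deaths censored, the plot does not show that. If one arm has more deaths on support, the survival results will not show the imbalance and may move the wrong way. No survival version is planned that would reveal this.

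**Working it through.** **Inputs.** 95 children per group enrolled, 92 needed; planning means 44 and 14 h with SD 50 (SAP 1.3). Placebo mean 44.4 and SD 63.62 h (Protocol 7.2, Table 2). Horizon 28 × 24 = 672 h. The documents give no mortality rate. Protocol 1.5 reports no adverse event leading to death in CIT-002-01, and 0 of 22 has an upper 97.5% limit of 1 − 0.025^(1/22) ≈ 15%. The numbers and times of deaths below are therefore assumptions.

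**The plan's own figure.** With effect size 30/50 = 0.600, p = Φ(0.6/√2) = 0.6643. Noether's formula gives n = (2.576 + 1.282)² / [6 × (0.6643 − 0.5)²] = 91.85, so 92 per group, as stated. This number does not depend on how deaths are handled.

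**Step 1: the curve.** Suppose k of 95 children die on support and nearly all others are off support by Day 28. The true proportion off support is (95 − k)/95, while one minus Kaplan-Meier goes to nearly 1. The gap is about k/95: 1.05, 2.11 and 4.21 points for k = 1, 2 and 4. A simulation (lognormal with the Table 2 placebo mean and SD, capped at 672 h, death probability proportional to time on support) gives about 1.0, 2.0 and 4.0 points. The binomial standard errors of (95 − k)/95 are 1.05, 1.5 and 2.1 points. At 48 h the gap is only about 0.3 to 1.5 points against a standard error of 4.6.

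**Step 2: log-rank.** Simulation of 1,500 trials per row, 92 per arm, both arms lognormal with mean 44 and SD 50 h (no true effect). There are k extra deaths on support in the L-citrulline arm at 6 to 48 h. Positive z favours L-citrulline. The last two columns give the chance of z > 1.96; the nominal value is 2.5%.

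| Who dies | k | Mean z, censored at death | Mean z, kept to 672 h | Favourable, censored | Favourable, kept |
|---|---|---|---|---|---|
| Random among those on support | 0 | +0.01 | +0.01 | 3.3% | 3.3% |
| | 1 | −0.02 | −0.33 | 2.3% | 0.9% |
| | 3 | −0.02 | −0.80 | 2.9% | 0.1% |
| | 5 | −0.03 | −1.19 | 2.7% | 0.0% |
| Longest-stay children | 0 | −0.02 | −0.02 | 2.3% | 2.3% |
| | 1 | +0.27 | −0.09 | 5.1% | 1.5% |
| | 3 | +0.71 | −0.30 | 12.4% | 0.6% |
| | 5 | +1.08 | −0.48 | 19.3% | 0.2% |

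The two k = 0 rows are the same setting, so 3.3% against 2.3% shows the simulation noise. When deaths are random, the censored test does not see them. When the sickest die, it moves towards the arm with more deaths.

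**Step 3: Cox.** 95 per arm, lognormal with log-means 3.0 (L-citrulline) and 3.3 (placebo) and log-SD 1.0. A hazard ratio above 1 favours L-citrulline.

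- Three L-citrulline deaths against none, probability proportional to time on support: 1.32 if nobody had died, 1.32 with deaths censored, 1.15 with deaths kept to 672 h.
- None against three: 1.32, 1.32 and 1.42.
- Three L-citrulline deaths among the longest-stay children: 1.33 if nobody had died, 1.39 with deaths censored.

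**The case against.** Three points on the other side have force.

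**The Wilcoxon test has its own check.** A reader might infer that the plan has no analysis in which death counts as failure to come off support. That holds only within the survival analyses. SAP 4.4.1 keeps the 28-day rule for the Wilcoxon test of the same composite, and that check responds to deaths. With five random extra deaths in the Step 2 setting, mean Wilcoxon z goes from +0.33 with observed lengths to −0.39 with 28 days. Deaths by arm are also reported.

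**Censoring death is a recognised choice.** A reader might infer that the log-rank and Cox results are invalid, and take the move from 1.32 to 1.15 as bias. Step 3 does not support this. When deaths are spread in proportion to time on support, the censored hazard ratio equals the death-free one. The move is mostly a change of question, from the cause-specific hazard to coming off support alive. Distortion appears when those who die are the longest-stay children. Only the curve, read as a probability, is too high whoever dies.

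**Hospital and PICU stay.** Read literally, the censoring sentence names only ventilation and inotropes, so a reader might infer that a death off support counts as a discharge. The sentence was written for the composite, and no text calls a death a discharge. SAP 4.4.2 also gives these endpoints their own exclusion and 28-day rules. What stands is that the event and the censoring rule are not stated for them.

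The protocol does not say outright that the death rules extend to the survival analyses. The SAP sentence is an unlisted restriction rather than a plain contradiction.

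**Conclusion.** The point holds as a limited one. SAP 4.4.1 censors death on support at the day of death and withdraws the 28-day rule for Kaplan-Meier, log-rank and Cox, and SAP section 5 does not list the withdrawal. As a result, no survival analysis estimates the probability of coming off support alive.

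The curve is too high by about 1 point per death per 95 children by Day 28. The censored log-rank test does not react to excess deaths on support. With five extra deaths among the longest-stay children, it favours the arm with more deaths in 19.3% of trials with no true effect.

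These sizes rest on assumed death counts, death times and lognormal durations. With no deaths the two rules agree; with one death the shift in mean log-rank z is at most +0.27. The primary conclusion does not depend on these analyses, and the sample size is unchanged. This is a cheap improvement to sensitivity analyses, not a fault in the primary test.

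**What to change.** In SAP 4.4.1:

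1. Delete the withdrawal of rule (2) for the survival analyses. If it is kept, list it in SAP section 5 with a reason.
2. Add a version of the Kaplan-Meier, log-rank and Cox analyses in which a child who dies on support stays at risk to Day 28 and is censored at 672 h. Apart from early withdrawals, the complement of the curve is then the cumulative incidence of coming off support alive, and the Cox model is the matching subdistribution model.
3. Keep the death-censored version beside it, labelled as cause-specific. Neither needs to replace the other.
4. Tabulate deaths on support by arm.
5. Say how a child who dies after support has ended is handled in the new version. Rule (2) as worded covers every death, while the censoring sentence covers only deaths on support.

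In SAP 4.4.2, for PICU and hospital stay, state that the event is discharge alive. An in-hospital death follows the same rule and is not counted as an event.

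The cost is a few sentences, one changed censoring variable and one extra set of outputs. No new data are needed. The subdistribution hazard ratio is less familiar to readers. The rule should be settled before unblinding, while deaths by arm are unknown.

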4.4.2 Analysis of Secondary Efficacy Variables

No formal statistical hypotheses are specified for the secondary endpoint variables. Nonetheless statistical testing methods will be applied to compare treatment groups. A significance level of 5% (two-sided) will be used for such analyses. Secondary efficacy endpoints will be analyzed using FAS, mFAS and PP. All secondary analyses are considered exploratory.

Length of time on mechanical ventilation

The same definitions and analyses as described for the primary endpoint will be applied. As sensitivity analysis, length of time on mechanical ventilation will be calculated starting on “start date/time” of mechanical ventilation.

Length of time on positive pressure (non-invasive) ventilation

Positive pressure ventilation describes non-invasive mechanical ventilation. The same definitions (only using non-invasive ventilation stop date/time and non-invasive ventilation breaks: BPAP, CPAP, HFNC, and other non-invasive) and analyses as described for the primary endpoint will be applied.

Length of time of inotrope use

The same definitions and analyses as described for the primary endpoint will be applied. As sensitivity analysis, length of time of inotrope use will be calculated starting on first “start date/time” of inotrope use.

Inotrope score

The total inotrope score at each hour post-operatively from the time of separation from bypass until the completion of study drug will be calculated as:

Total Inotrope Score = Dopamine + Dobutamine + 10*Milrinone + 100*Epinephrine +100*Phenylephrine + 100*Norepinephrine.

The score will be calculated for each hour post separation from CPB (see section 4.4.1) until 48 hours post separation. If within the time interval of hours x after the separation from CPB any inotrope was given, the total score will be calculated and used for analysis.

Example for a patient's inotrope documentation:

- 12:00: Separation from CPB
- Dopamine: 100 mcg/kg/min from 12:00 to 13:00,
- Dobutamine 100 mcg/kg/min from 13:00 to 13:30, 14:01 to 14:59, and 16:00 to 17:00.

The times of interest at 1, 2, 3, ... hrs will be derived as time of separation from CPB + 59, 119, 179, ... minutes. I.e., the times of interest and the total inotrope score would then be calculated as follows:

- 1 hrs (12:00-12:59) = 100 (Dopamine (100) documented 12:00-13:00)
- 2 hrs (13:00-13:59) = 200 (Dopamine (100) documented 12:00-13:00
Dobutamine (100) documented 13:00-13:30)
- 3 hrs (14:00-14:59) = 100 (Dobutamine (100) documented 14:01-14:59)
- 4 hrs (15:00-15:59) = 0 (no inotropes documented 15:00-15:59)
- 5 hrs (16:00-16:59) = 100 (Dobutamine documented 16:00-17:00)
- 6 hrs (17:00-17:59) = 100 (Dobutamine documented 16:00-17:00)
- 7 hrs (18:00-18:59) = 0 (no inotropes documented 17:01-18:00)
- ...

The total inotrope score will be imputed to zero after the bypass pump has been removed (separation from CPB). It will also be imputed as zero for patients not using inotropes at all.

The total inotrope score will be summarized at each post-operative hour and analyzed using a Wilcoxon-Rank sum test and an analysis of variance (ANOVA) with a fixed effect for treatment group. Additionally, a repeated measures analysis of variance will be used to compare total inotrope score between placebo and L-citrulline over time.

Hemodynamic improvement

Hemodynamic evaluations include heart rate, systemic arterial blood pressure, oxygen saturation, and central venous pressure. The absolute changes from Baseline at hours 1, 2, 4, 12, 24, and 48 will be compared between groups using an ANOVA with a fixed effect for treatment group and Baseline level.

The last non-missing hemodynamic assessment before start of surgery will be used as Baseline level; i.e. "Date and time of assessment" from section "Hemodynamics" on CRF "Hemodynamics" before "Date of surgery" and "Start time (incision time)" from section "Surgery" on CRF "Surgery". Documented assessments as closest to the target hours 1, 2, 4, 12, 24, and 48 using the following analysis time windows will be used for analysis:

- 1 hrs = 1 min to 89 min (>0 hrs to <1.5 hrs)
- 2 hrs = 90 min to 179 min (≥1.5 hrs to <3.0 hrs)
- 4 hrs = 180 min to 479 min (≥3.0 hrs to <8.0 hrs)
- 12 hrs = 480 min to 1079 min (≥8.0 hrs to <18.0 hrs)
- 24 hrs = 1080 min to 2159 min (≥18.0 hrs to <36.0 hrs)
- 48 hrs = 2160 min to 3599 min (≥36.0 hrs to <60.0 hrs)

An ANOVA per hour adding site and site-by-treatment group interaction will be conducted as a sensitivity analysis. If the p-value for the site-by-treatment group interaction is lower than 0.1 the analysis will also be provided by site. Absolute values and absolute change from Baseline values will be summarized for all observed time points.

Length of time on intubation (invasive ventilation)

The same definitions (only using invasive ventilation stop date/time and invasive ventilation breaks: FVS, PVS and other invasive) and analyses as described for the primary endpoint will be applied.

Length of PICU stay

The length of PICU stay will be calculated as the total number of days postoperative until discharge from PICU. The length will be derived as the number of days from day after surgery (variable "Date of surgery" on CRF "Surgery" + 1) until discharge from PICU (variable "Date transferred to floor" on CRF "Post-operative observation"). If subject has to be readmitted to PICU, time will continue to accrue (variables "Date of readmission" and "Date transferred to floor" (second assessment) from CRF "Post-operative observation").

- Length of PICU stay (days) =
(Date transferred to floor - (Date of surgery + 1) + 1) +
(Date transferred to floor (2nd assessment) - Date of readmission + 1)

For subjects who died before discharge from PICU or before Day 28, respectively, the observed length of PICU stay will be used. As sensitivity analyses subjects who died will (1) be excluded from analysis and (2) be assigned a length of PICU stay of 28 days.

For the length of PICU stay the same analyses as described for the primary endpoint will be applied.

Length of time on vasodilators

Length of time on vasodilators will be measured from first use following separation from bypass, until the subject is discharged from the hospital or at Day 28. The length will be derived as the time in minutes from separation from CPB (variable "End time" of parameter "CPB" from section "Post incision" on CRF "Surgery") until last use (last "end date/time" of any medication as documented in sections "Vasodilators" or "Other vasodilators" on CRF "Inotropes and Vasoactive Medications").

- Length of time of vasodilators (min) =
Last "end date/time" of any vasodilators - End time (CPB) + 1

Any interruptions will discontinue to accrue, any duration of re-use of vasodilators will continue to accrue. If a subject did not use any vasodilators the length is set to 0. As a sensitivity analysis, subjects with no use of vasodilators will be excluded. For subjects who died before discharge from the hospital or before Day 28, respectively, the observed length of time on vasodilators will be used. As sensitivity analyses subjects who died will (1) be excluded from analysis and (2) be assigned a length of time on vasodilators of 28 days.

For the length of time on vasodilators the same analyses as described for the primary endpoint will be applied.

Length of hospitalization

The length of hospitalization will be calculated as the total number of days postoperative until discharge from the hospital. The length will be derived as the number of days from day after surgery (variable "Date of surgery" on CRF "Surgery" + 1) until discharge from the hospital (variable "Hospital Discharge date" on CRF "End of study").

- Length of hospitalization (days) =
Hospital Discharge date - (Date of surgery + 1) + 1

For subjects who died before discharge from the hospital or before Day 28, respectively, the observed length of hospitalization will be used. As sensitivity analyses subjects who died will (1) be excluded from analysis and (2) be assigned a length of hospitalization of 28 days.

For the length of hospitalization, the same analyses as described for the primary endpoint will be applied.

Thoracotomy output - duration and volume of chest tube drainage

The total postoperative duration (in minutes) that the chest tube will be used will be calculated as the time from the end of the surgery (variables "Date of surgery" and "End time" from section/CRF "Surgery") to the time the chest tube will be removed (variable "Date/time of removal" from section/CRF "Thoracotomy Output").

If an additional chest tube is required or reinserted (until discharge from the hospital or at Day 28) the duration that the additional chest tube was used (from time of insertion to time of removal) will be added to the time the original chest tube was used for the total postoperative duration.

- Length of chest tube drainage (min) =
(Time removal - End time (surgery) + 1) +
(Time removal (second assessment) - Time reinsertion + 1)

If a subject did not use any chest tube the duration is set to 0. As a sensitivity analysis, subjects with no use of chest tube will be excluded. For subjects who died before discharge from the hospital or before Day 28, respectively, the observed duration of chest tube drainage will be used.

For the total postoperative duration, the same analyses as described for the primary endpoint will be applied.

Again, as sensitivity analyses subjects who died will (1) be excluded from analysis and (2) be assigned a length of time of chest tube placement of 28 days.

The total amount of chest tube drainage (mL), adding up each duration of chest tube as described above, will be summarized using descriptive measures and compared between groups using an ANOVA with a fixed effect for treatment group.

L-citrulline plasma levels

L-citrulline plasma levels will be obtained on each patient at set times. Individual concentration-time curves will be plotted to confirm that they are \geq the threshold level of 100 $\mu\text{mol/L}$. In addition, summary statistics using descriptive measures will be tabulated.

